8.2 Study Hypotheses

The above considerations motivate multiple hypotheses. As pre-specified below, Hypothesis 1 tests Imagio specificity superiority versus IUS (H1) while Hypothesis 2 tests Imagio sensitivity non-inferiority versus IUS (H2). Hypotheses 3 and 4 test if the stand alone Imagio specificity is at least 40% (H3) and the stand alone sensitivity is at least 90% (H4). Hypothesis 5 tests the hypotheses for using Imagio to downgrade benign masses to BI-RADS 2 and 3 from BI-RADS 3, 4a, and 4b using IUS (H5) and upgrade malignant masses relative to IUS (H6).

The study hypotheses are as follows:

8.2.1. Hypothesis 1: The Imagio specificity is superior to IUS specificity

Null hypothesis) Ho: Imagio specificity – IUS specificity < 0%

versus

Alternative hypothesis) Ha: Imagio specificity – IUS specificity > 0%

A 6% absolute advantage in specificity is regarded as being the minimum meaningful advantage to help spare biopsies. Specificity superiority will be tested against the null hypothesis of no difference.

8.2.2. Hypothesis 2: The Imagio sensitivity is non-inferior to IUS

Null hypothesis) H_0 : Imagio sensitivity – IUS sensitivity \leq -5%

versus

Alternative hypothesis) H_a: Imagio sensitivity – IUS sensitivity > -5%

Sensitivities are expected to be at least 95% for both Imagio and IUS. A 5% sensitivity non-inferiority margin is regarded as being clinically meaningful.

8.2.3. Hypothesis 3: Imagio has acceptable stand-alone specificity

Null hypothesis) Ho: Specificity = 40%

versus

Alternative hypothesis) Ha: Specificity > 40%

Seno Clinical Study Protocol: PIONEER-01 300176 Rev 8 PIONEER 01 Protocol Amendment 3.2 Eff. Date: October 15. 2015 Confidential Page 53 of 80

A stand-alone specificity exceeding 40% is regarded as being clinically meaningful.

8.2.4. Hypothesis 4: Imagio has acceptable stand-alone sensitivity

Null hypothesis) H_0 : Sensitivity = 90%

versus

Alternative hypothesis) Ha: Sensitivity > 90%

A stand-alone sensitivity exceeding 95% is regarded as being clinically meaningful.

8.2.5. Hypothesis 5: Imagio evaluation improves the overall diagnostic efficiency for benign masses as measured by the relative risk in the BI-RADS 3 and BI RADS 4a and BI RADS 4b subgroups according to IUS. A reduction of BI-RADS 4a and BI-RADS 4b according to IUS to BI-RADS 2 or 3 according to Imagio would be a major advance as would a reduction of BI-RADS 3 according to IUS to BI-RADS 1 or 2 according to Imagio. Specifically, the cancer prevalence ranges from 2% to 10% for the BI-RADS 4a category and 11% to 50% for the BI-RADS 4b category so a reduction to 1% or 2% would be equivalent to BI-RADS 2 or 3 which would be sufficient to prevent negative biopsies and to delay interval follow-up. A similar benefit would be to reduce cancer prevalence from 2% to <2% for the BI-RADS 3 subgroup.

Null hypothesis) H_o: No difference in BI-RADS according to Imagio vs. IUS

versus

Alternative hypothesis) H_a: Decreased BI-RADS according to Imagio vs. IUS

A 25% reduction to BI-RADS 2/3 from BI-RADS 3/4a/4b is regarded as being clinically meaningful for benign masses.

8.2.6. Hypothesis 6: Imagio evaluation improves the overall diagnostic efficiency for malignant masses as measured by the relative risk in the BI-RADS subgroups according to IUS. An increase in BI-RADS according to IUS to higher BI-RADS according to Imagio would be a major advance.

Null hypothesis) H_o: No difference BI-RADS according to Imagio vs. IUS

versus

Alternative hypothesis) H_a: Increased BI-RADS according to Imagio vs. IUS

A 10% increase in BI-RADS 3/4a/4b/4c to higher BI-RADS 4c/5 is regarded as being clinically meaningful for malignant masses.

8.3. Analysis Populations

Seno Clinical Study Protocol: PIONEER-01
300176 Rev 8 PIONEER 01 Protocol Amendment 3.2

Confidential Page 54 of 80

All analyses will be performed with the intention to diagnose (ITD) study population which consists of all subjects coming in for their scheduled Imagio evaluation, having Imagio data declared evaluable, and having a biopsyat 12 months, or declared to be TN (or FP) at 12months.

There will be Truth Panel review to identify mass-specific subgroups and TN outcomes as well as reader-specific exclusions for the following:

- 1. Cases with QAR concerns (including cases with previously unidentified suspicious masses and cases where the Imagio evaluation was incomplete, unreliable, or unusable) for exclusions
- 2. Cases where the number or numbering of suspicious masses is under dispute (per QARs or IRs) for exclusions
- 3. Cases with questionable eligibility for exclusions
- 4. Cases with high risk histologies for separate analyses
- 5. Cases where individual IRs identified problems with specific image sets for exclusions
- 6. Cases with NDUs to determine if a mass was a True-Negative (TN) for specificity calculations.

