The Pilot Study (Pilot Phase of the Pivotal Study) data will be used to validate the existing algorithm to a pre-determined diagnostic rule set based on OA image characteristics established in a previously conducted independent Feasibility Study. The Pilot Study will collect imaging data from 100 subjects passing Quality Assurance review conducted by three central radiologists blinded to clinical history and histopathology outcome. Then a pool of at least 20 other independent radiologists (readers) not affiliated with any sites will be prospectively trained and then tested for proficiency using the image sets constructed by the central radiologists using the last 70 of the 100 Pilot cases. The first 30 cases will be used to familiarize readers with the image sets, the viewing logistics, and the eCRF to be completed, prior to reader proficiency testing. Upon establishing and meeting prospective rules for proficiency (based on Imagio sensitivity [missing at most one cancer] and Imagio specificity ≥30% after excluding the first 30 cases to allow for learning), a subset of 7 proficient readers will be selected for purposes of reading IUS and Imagio OA and 3 other readers will be selected to share the reimbursement reads of multiple combinations of imaging modalities with or without Imagio, The registration readers will be selected at random based on availability and once all readers are tested for proficiency; reimbursement readers will be selected by the Seno Medical Director. All registration readers will be proficiency tested and selected prior to making any Pivotal Study i.e., reads for subjects 101 and beyond, which will constitute the Pivotal Study. All effectiveness analyses will be conducted at the mass-level; it is projected that no more than 5% of all subjects will have multiple masses. A minimum of 100 Pilot Study masses and at least 1,700 Pivotal Study masses passing QA review and excluding enrollment failures are to be included. Enrollment will continue until there are 100 Pilot Study masses and at least 1,700 Pivotal Study masses that pass both criteria. The 100 Pilot Study cases will be used for education, training, and publication purposes; only the Pivotal Study cases will be used to support Imagio registration for this indication for use. All selected registration readers will evaluate all masses according to a MRMC design. To mimic the real world setting as closely as possible, all readers will receive feedback on the histopathology results in read only mode following their case reads after completing their locked evaluations; readers may not change results after receiving feedback. For the Pivotal Study, subsets of 5% of registration image sets and 2.5% of all reimbursement image sets will be reread to assess learning and consistency; the first reads will be used in the data analyses for registration and reimbursement. The PMA filing will be based

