4. STUDY POPULATION SELECTION

4.1. Study Population

At least 2,000 subjects will be prospectively enrolled upon confirmation of being BI-RADS 3, BI-RADS 4, or BI-RADS 5 to obtain a sufficient number of benign masses (at least 1,000 masses) and, if there is not a sufficient number, then the total number of subjects may increase slightly to achieve the target number for benign masses. The following masses will be considered enrollment failures:

(a) masses for which the investigational device scans do not pass review (QAR failures) for Independent Review, or

Seno Clinical Study Protocol: PIONEER-01 300176 Rev 8 PIONEER 01 Protocol Amendment 3.2

(b) masses that have incomplete investigational device scans due to device malfunction, subject withdrawal or lesion being too deep for Imagio visualization.

Subjects with an undiagnosed suspicious finding within the previous 45 business days, by palpation or by a screening or diagnostic methodology other than ultrasound will be prospectively screened and consented. Once the investigator has made a biopsy decision (either no or yes), subjects will undergo an Imagio evaluation.

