8.5. Analysis Definitions

The final data for diagnostic test sensitivity and specificity will be presented in terms of a 2×2 table as follows; the threshold for defining a positive POM will be 2% corresponding to clinical practice standards:

Table 5: 2 x 2 Table

	Cancer	Benign
Test +	True Positive (TP)	False Positive (FP)
Test -	False Negative (FN)	True Negative (TN)

The above 2x2 table will also be constructed separately for Imagio and the Imagio diagnostic ultrasound component relative to a cancer or benign diagnosis. In addition, these 2x2 tables will also be generated for immediate biopsies, for delayed biopsies, for all biopsies, and for all cases including those not biopsied; discordant pairs for sensitivity as well as specificity will be analyzed. Those subjects without a biopsy will be excluded if they were not followed without a subsequent clinical evaluation.

A subject will be assigned to a row in the table depending on the respective diagnostic test result. Subjects with a diagnosis (biopsy or 11 month follow-up with no biopsy) will be assigned a column in the table according to the following rules:

- 1. If the result of the biopsy results in a cancer diagnosis, then the subject will be assigned to the Cancer column.
- 2. If the result of the biopsy results in a benign diagnosis, then the subject will be assigned to the Benign column.
- 3. If the biopsy was not performed and the subject was evaluated after 11 months post-baseline (nominal 12 month evaluation), then the subject will be counted as TN as long as there were no contrary clinical or radiologic findings (not to be based on Imagio); any mass declared to have any contrary clinical or radiologic findings will be declared to be a False-Positive if the Imagio POM was ≤2%; otherwise the subject will not be included in the table
- 4. If the baseline Imagio evaluation was not performed or declared to not be useable, then the subject will not be included in the table.

In addition, the cancer group will be further divided into invasive carcinoma and DCIS categories and each of these two categories will be assessed separately within a 2x2 table.

The use of the terms *sensitivity* and *specificity* is justified in this study because the biopsy and 11 month evaluation (12 month nominal evaluation) is the gold standard. The following statistical endpoints will be assessed for each image set:

- The true positive rate (TPR) or sensitivity of the test is defined as TP/ (TP + FN)

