8.8. Other Assessments or Analyses

Specific treatment-emergent adverse events will also be displayed for each subject.

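### Section 8.3 puts all analyses, and so read literally the safety analysis, in a set that requires an evaluable scan and a final diagnosis, in conflict with the adverse event rules in Section 6.5

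*Protocol*

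**What the plan says.** Section 8.3 opens with "All analyses will be performed with the intention to diagnose (ITD) study population" and admits subjects who attend the Imagio visit, subject to "having Imagio data declared evaluable, and having a biopsyat 12 months, or declared to be TN (or FP) at 12months". I read the biopsy condition as a biopsy by 12 months. The section also sends to the Truth Panel, for possible exclusion, "cases where the Imagio evaluation was incomplete, unreliable, or unusable".

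Section 4.1 names two kinds of enrollment failure. One is "masses for which the investigational device scans do not pass review (QAR failures) for Independent Review"; the other is "masses that have incomplete investigational device scans due to device malfunction, subject withdrawal or lesion being too deep for Imagio visualization". Section 8.5 adds: "Those subjects without a biopsy will be excluded if they were not followed without a subsequent clinical evaluation". I take this to mean unbiopsied women with no later clinical evaluation.

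Safety is objective 7 in Section 2. The only safety output in Section 8 is one sentence in Section 8.8: "Specific treatment-emergent adverse events will also be displayed for each subject". It names no population.

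Sections 6.5.4 and 6.5.6 say that every adverse event must be recorded so that it can be analysed and the findings put in the study report. Section 6.5.5 requires serious events and unanticipated device effects to be reported from consent onward. None of the three sets a condition on image quality or final diagnosis.

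**The concern.** The conditions for entering the analysis set make sense for sensitivity and specificity, which need a readable image and a reference diagnosis. They do not suit adverse events. Whether a woman felt warmth or tingling on the day of the scan has nothing to do with whether the image passed review or whether she returned a year later. Yet, on the literal text, those later facts decide whether her event is analysed.

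Some of the exclusions may also be linked to the outcome. A woman who withdraws during the scan, or whose scan ends in a malfunction, may be more likely than others to have had discomfort or a device effect. Section 6.6 also lets the investigator withdraw a subject for her safety; if that happens before a biopsy or a 12-month call, she leaves the only defined set. An adverse event rate computed in that set could then be too low, in support of a stated objective of the study.

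**Working it through.** **1. The passages side by side.**

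| Question | Section 8.3 | Sections 6.5.4 to 6.5.6 | Section 8.8 |
|---|---|---|---|
| Whose adverse events are analysed? | Only subjects with evaluable Imagio data and a final truth | All adverse events recorded for analysis and reported; serious events and device effects from consent | Displayed per subject; no population named |

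The protocol limits a rule to effectiveness elsewhere: the Synopsis and Section 3.2 apply the mass-level rule to effectiveness analyses only. Section 8.3 has no such limit. The two rules cannot both be followed, and Section 8.8 does not choose between them.

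**2. The stated safety figure.** Section 5.6 gives a discomfort risk of 0.4%, or 1:269. Check: 1/269 = 0.372%, which rounds to 0.4%. It reproduces.

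**3. How many women might fall outside.** Inputs: at least 2,000 women enrolled (Synopsis); at least 100 Pilot and 1,700 Pivotal masses passing quality review (Synopsis), so 1,800 masses.

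- One mass per woman, all women scanned, Pilot women counted in the 2,000: 2,000 − 1,800 = 200, or 10%.
- If 5% of women have two masses: 1,800/1.05 = 1,714 women, leaving 286, or 14%.

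Women without a final truth would add to this; the protocol gives no figure. Both inputs are minimums, and one counts women while the other counts masses, so these numbers are indicative only.

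**4. Effect on the rate.** Expected events at 1:269: 2,000/269 = 7.4 in all; 1,800/269 = 6.7 among evaluable women; 200/269 = 0.74 among the rest, if the rate is uniform.

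Hold the total at 2,000/269 = 7.43 and let the 200 omitted women have m times the rate of the 1,800 evaluable women. The rate in the evaluable set is 7.43/(1,800 + 200m), and the share of events omitted is 200m/(1,800 + 200m).

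| m (assumed) | Rate in evaluable set | Share of events omitted |
|---|---|---|
| 1 | 7.43/2,000 = 0.37% | 10% |
| 2 | 7.43/2,200 = 0.34% | 18% |
| 5 | 7.43/2,800 = 0.27% | 36% |
| 10 | 7.43/3,800 = 0.20% | 53% |

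With m = 1 some events are lost but the rate is unbiased.

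**5. Precision.** With zero events of a given kind, the one-sided 95% upper bound, 1 − 0.05^(1/n), is 0.166% for n = 1,800 and 0.150% for n = 2,000. The loss of precision is small; the issue is possible selection.

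**The case against.** The best reply is that the protocol already covers safety. Sections 6.5.4 and 6.5.6 speak of analysis and reporting, not only collection. Section 8.8 refers to each subject and not to the ITD population, the term Section 8.4 uses when it means that set. The conditions in Section 8.3 (truth status, reader exclusions, specificity) point to effectiveness, and a safety set is often left to the SAP. Safety is descriptive here: none of the six hypotheses in Section 8.2 concerns it, and the device was judged non-significant risk.

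Much of this stands. No adverse event goes uncollected and no registration test changes. It does not remove the conflict. Section 8.3 makes a positive statement about all analyses, and Section 9.12 ties the SAP to the protocol's statistical section, so a separate safety set in the SAP would depart from Section 8.3 as written. A per-subject display also supplies no denominator or incidence.

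The link to tolerability is plausible but not documented. Section 5.6 says the discomfort resolves at once when the scan ends; it does not say that it stops scans. Review failure and lesion depth have no stated link to tolerability, and Sections 6.2.2 and 6.2.3 allow a repeat scan before biopsy, so some failures re-enter.

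Two stronger readings are tempting and should be set aside:

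- A reader might infer that Section 8.3 removes the 100 Pilot subjects from safety. It does not mention them, and a Pilot subject with evaluable data and a final truth meets its definition. The statement that "only the Pivotal Study cases will be used to support Imagio registration for this indication for use" concerns support for registration, not adverse event reporting.
- A reader might infer that the reported rate could fall to zero. That would need all of the roughly 7 expected events to lie among the omitted women. If half did, about 3.7/1,800 = 0.21% would remain.

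**Conclusion.** The point holds as an internal conflict with a possible bias, not as an unopposed exclusion. As written, Section 8.3 confines the safety analysis to women with an evaluable scan and a final truth, while Sections 6.5.4 to 6.5.6 require adverse events to be analysed or reported without those conditions.

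Any bias would be downward, through withdrawal and malfunction. Its size cannot be determined from the protocol, which gives no count for either. The illustrative range, from no bias up to 0.20% read in place of 0.37%, rests on 200 omitted women, a total fixed by the 1:269 rate, and rate ratios that I have assumed. The correction should be made, but it does not bear on the specificity or sensitivity tests.

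**What to change.** Three edits:

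1. In Section 8.3, restrict the opening sentence to effectiveness analyses.
2. In the same section, define a safety population: every subject with any Imagio exposure at any visit, regardless of quality review result, scan completion, withdrawal or truth status. State that Pilot subjects are included.
3. In Section 8.8, state that the incidence of adverse events, serious adverse events and unanticipated adverse device effects is reported in that population with exact confidence limits, consistent with Sections 6.5.4 to 6.5.6.

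The cost is a few sentences. Section 6.5 already requires the events to be captured from consent, so no new data are needed.

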All registration readers will be tested and selected prior to making any further Pivotal Study reads for subjects 101 and beyond which will constitute the Pivotal Study. All effectiveness analyses will be conducted at the mass-level; it is projected that no more than 5% of all subjects will have multiple masses. A minimum of 100 Pilot Study cases and 1,700 Pivotal Study cases must pass QA review and must not be enrollment failures to be included in the respective Pilot and Pivotal Study analyses. Enrollment will continue until there are 100 Pilot Study cases and at least 1,700 Pivotal Study cases that pass both criteria. The 100 Pilot Study cases will be used for education, training, and publication purposes; only the Pivotal Study cases will be used to support Imagio registration for this indication for use.

All selected registration readers will evaluate all masses that pass QA review according to a MRMC design for the pivotal phase. To mimic the real world setting as closely as possible, all readers will receive respective feedback on the histopathology results after completing their locked evaluations; readers may not change results after receiving feedback.

For the Pivotal Study component, subsets of 5% of registration image sets and 2.5% of all reimbursement image sets will be reread to assess learning and consistency; the first reads will be used in the data analyses for registration and reimbursement. Readers will be required to turn in their evaluations before conducting the rereads which will be conducted once the respective reader completes their Pivotal Study reads.

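### The set labelled intention to diagnose is an evaluable-only set, so stand-alone specificity (H3) is estimated only among masses with a usable Imagio scan

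*Protocol*

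**What the plan says.** Protocol 8.3 assigns all analyses to one intention-to-diagnose population: "all subjects coming in for their scheduled Imagio evaluation, having Imagio data declared evaluable", with truth known from biopsy or 12-month follow-up. It then lists case types that go to Truth Panel review. Two of them matter here: "cases where the Imagio evaluation was incomplete, unreliable, or unusable) for exclusions" and "Cases where individual IRs identified problems with specific image sets for exclusions". The lead-in to that list calls some of these exclusions reader-specific.

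Section 4.1 defines two kinds of enrollment failure: "masses for which the investigational device scans do not pass review (QAR failures) for Independent Review" and "masses that have incomplete investigational device scans due to device malfunction, subject withdrawal or lesion being too deep for Imagio visualization". Section 3.2 says that cases "must pass QA review and must not be enrollment failures to be included in the respective Pilot and Pivotal Study analyses". Both the synopsis and 3.2 continue enrollment until 100 Pilot and at least 1,700 Pivotal masses pass, so failures are replaced. Rule 4 of the 2×2 table in 8.5 adds: "If the baseline Imagio evaluation was not performed or declared to not be useable, then the subject will not be included in the table".

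Sections 6.2.2 and 6.2.3 allow a repeat scan if image quality is unacceptable and no biopsy has been done. Section 5.13 gives the Truth Panel access to all clinical data and to the independent readers' results.

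**The concern.** An intention-to-diagnose set keeps every mass that the test was meant to diagnose, including those on which the test gave no answer. The set in 8.3 drops them, so its name and its definition disagree.

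The benefit claimed for the device is fewer biopsies of benign masses. A benign mass with no usable Imagio result gets none of that benefit, yet it leaves the denominator of specificity. These losses are also unlikely to be random: depth is a property of the lesion, and a repeat scan may not cure it. In addition, the panel that reviews exclusions can see clinical data and reader scores, so the exclusions are not protected from knowledge of the outcome.

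The hypothesis most exposed is H3, which tests stand-alone specificity against a fixed 40%.

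**Working it through.** **Inputs.** From Protocol 8.6, Table 8: null specificity 40%, alternative 45%, one-sided 99.5% exact bound, 80% power, 1,160 benign masses. From Table 6: 6-point difference, 20% discordant, 860 benign masses, 90% power. From Table 9: sensitivity 95% against a 90% null. The failure fraction f is not in the documents; 2%, 5% and 10% are assumptions.

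**The plan's own figures.** For H3, the smallest count r with P(X ≥ r | n = 1,160, p = 0.40) ≤ 0.005 is 508, and 508/1,160 = 43.8%. Power is P(X ≥ 508 | p = 0.45) = 80.4%, so Table 8 reproduces. For H1, the McNemar formula at one-sided 0.5% needs 822 pairs, or 839 with continuity correction, against 860 stated. Power at 860 is 91.5%. The stated sizes are therefore sound as counts of evaluable masses.

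**H3 with failed benign masses counted as not cleared.** Specificity = 45% × (1 − f). For power, the 1,160 evaluable masses are kept, n = 1,160/(1 − f), and the exact cut-off is recomputed.

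| f | Specificity | n | H3 power |
|---|---|---|---|
| 0% | 45.0% | 1,160 | 80% |
| 2% | 44.1% | 1,184 | 61% |
| 5% | 42.8% | 1,221 | 25% |
| 10% | 40.5% | 1,289 | 1% |

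Expected specificity reaches the 43.8% cut-off at f = 1 − 43.8/45 ≈ 2.7%, and the 40% null at f = 1 − 40/45 = 11.1%.

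**H4.** If failed cancers count as negative, sensitivity = 95% × (1 − f) = 93.1%, 90.3%, 85.5%. If they count as positive, it is 95% × (1 − f) + 100% × f = 95.1%, 95.3%, 95.5%. The direction depends on the counting rule.

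**H1, both reads fail and receive the same value.** Difference = 6 × (1 − f) = 5.9, 5.7, 5.4 points. Power stays near 91%.

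**H1, only opto-acoustics fails.** Assume a specificity of 39% for the ultrasound component (45% − 6). Difference = 45% × (1 − f) − 39% = 5.1, 3.8, 1.5 points. With discordance 20% × (1 − f) + 39% × f and n = 860/(1 − f), power is about 78%, 46% and 6%.

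**The case against.** The exclusions are prospective and consistent across sections. A repeat scan is possible. A statistical analysis plan, not shown here, could hold a bounding analysis. This stands in part: nothing is hidden, and the absence of a bounding analysis would not by itself be a finding. But the protocol itself fixes one set for all analyses and gives it a name that the definition contradicts.

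Four stronger readings are tempting, and the documents do not support them.

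- **Readers can drop difficult cases from their own denominator.** Sections 5.5 and 8.3 send reader-flagged problems to the Truth Panel. Readers flag; nothing gives them power to remove, and a problem with an image set is not the same as a difficult case.
- **The gap between 2,000 subjects and 1,800 masses is a planned 10% failure allowance.** Both are minimum counts, 8.1.1 speaks of at least 1,700 women, and 4.1 ties the 2,000 to reaching enough benign masses. It is headroom, not a failure rate.
- **Every exclusion is a device failure.** Withdrawal, questionable eligibility and disputed mass numbering are not.
- **The primary comparison is compromised.** The ultrasound component and Imagio come from the same examination. If both fail, H1 hardly changes.

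It is also fair to object that counting every failed scan as positive would flatter sensitivity. And masses that fail quality review never reach the independent readers (3.2 and 7), so they have no ultrasound read to pair with. Any remedy must deal with both points.

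**Conclusion.** The point holds for the label and for stand-alone specificity. Followed as written, the plan estimates H3 only among masses with a usable scan. Failures among benign masses of about 2.7% would bring an expected 45% down to the H3 cut-off, so the exclusion rule alone could decide that test. This rests on an assumed failure rate, on a true specificity of 45% among evaluable masses, and on treating a failed scan as not cleared.

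For H1 the effect is small unless opto-acoustics fails while the ultrasound component remains readable; that case also rests on the assumed 39%. For H4 the direction is open until a counting rule is set. The sample sizes in Tables 6 and 8 are not called into question. The change should be made, but it does not undermine the design.

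**What to change.** Rename the 8.3 population evaluable and keep the planned analyses on it. Add a supporting analysis of every mass presented for Imagio with known truth, under these rules:

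- **H3:** a non-evaluable benign mass counts as not cleared (false positive).
- **H4:** report both extremes, with all non-evaluable cancers positive and then all negative.
- **H1 and H2:** use the actual ultrasound-component read where one exists; otherwise give the ultrasound component and Imagio the same value.
- **Reader-specific exclusions:** apply the rule for that reader only.
- **Withdrawals, ineligible cases and mass-numbering disputes:** list separately and do not count as device failures.

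Decide exclusions blind to truth and reader scores, and tabulate them by reason, truth status and reader.

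The cost is one extra analysis on data already held, with no new scans or reads, and a blinded step for exclusion decisions. The supporting specificity will be somewhat less favourable than the evaluable figure.
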